#### 1.1.2. Molecular Formula

Axitinib, a substituted indazole derivative, is an oral, potent, and selective inhibitor of VEGF receptors 1, 2, 3. The molecular formula is C22H18N4OS with molecular weight of 386.47. The chemical name is

N-Methyl-2-[3-((E)-2-pyridin-2-yl-vinyl)-1H-indazol-6-ylsulfanyl]-benzamide:

Figure 1 Molecular Formula

#### 1.1.3. Phase 2 Clinical Trials of Single-Agent Axitinib in mRCC

Three Phase 2 studies have been conducted to explore the safety and efficacy of axitinib in mRCC patients.

## 1.1.3.1. Cytokine-Refractory mRCC Studies

The Phase 2 study (Protocol A4061012) enrolled 52 patients with mRCC who were refractory to cytokine treatment. Two complete responses (CRs) and 21 partial responders

(PRs) were observed, for an ORR of 44.2%. The median time to progression (TTP) was 15.7 months and the median OS was 29.9 months. 

Long-term survival data were collected via an observational study (Protocol A4061065).  Of the 52 patients, 35 died of progressive disease, 5 died of "unknown causes," 10 were alive, and 2 were lost to follow-up. Median follow-up for OS was 5.9 yrs. The 5-year survival rate was 20.6% (95% confidence interval [CI], 10.9–32.4%). Treatment-emergent, all-causality grade ≥3 adverse events for the 52 patients included diarrhea (19%), fatigue (19%), hypertension (17%), weight loss (8%), and dehydration, myocardial infarction, and stomatitis (6% each). Hypothyroidism (all grades) was observed in 23%. Comparing the characteristics of the 5-year survivors (n = 10) vs <5-year survivors (n = 40), the former had higher ORR (100% vs 30%), longer axitinib therapy duration (median 5.8 years vs 0.67 years), and better baseline PS (80% vs 53% with PS 0) but were of similar median age (57 vs 60), gender (80% vs 75% males), and risk factors (50% vs 40% with zero MSKCC factors).

Subsequently, the Phase 2 Study (Protocol A4061035) in Japanese patients with advanced RCC who were refractory to first line cytokine containing regimen was conducted.  64 patients were enrolled in this study. Based on the results from IRC, confirmed partial response was observed in 32 patients, and ORR was 50.0%. In addition, median PFS was 11 months as of data cutoff date (February 26, 2010).

## 1.1.3.2. Sorafenib- and Sunitinib-Failure mRCC Study

The third Phase 2 study (Protocol A4061023) enrolled 62 patients with mRCC who were refractory to sorafenib treatment. In addition to prior sorafenib, most of the patients received prior sunitinib and (or) other drugs before enrollment in this study. The analysis of all 62 evaluable patients indicates 14 PRs (23%) and a median PFS of 7.4 months. The median PFS for the 14 patients who failed both sunitinib and sorafenib was 7.1 months.

## 1.1.4. Comparative Effectiveness Phase III Study of Axitinib in second line mRCC

The primary objective of this pivotal Phase 3 (AXIS) study was to compare the PFS of patients with mRCC receiving axitinib vs another TKI, sorafenib, following failure of 1 prior systemic first-line regimen. The secondary objectives were to compare the OS and ORR of patients in each arm, evaluate the safety and tolerability of axitinib, estimate the duration of response (DR) of patients in each arm, and compare the FACT-Advanced Kidney Cancer Symptom Index (FKSI) and EuroQoL-5D (EQ-5D).

Between 15 September 2008 and 23 July 2010, a total of 723 patients with mRCC were randomized into this Phase 3 study, treated with either axitinib or sorafenib, and were followed for safety and efficacy. Enrolled patients were ≥18 years old, had histologically confirmed mRCC, had an ECOG PS of 0 or 1, and had failed 1 prior systemic, first-line regimen, which must have contained 1 or more of the following: sunitinib, bevacizumab + IFN-α, temsirolimus, or cytokine(s). Demographic and baseline characteristics were well balanced between both treatment arms.

The study enrolled 361 patients in the axitinib arm and 362 in the sorafenib arm. Based on the blinded IRC review of the overall analysis, the median PFS was 6.7 months (95% CI

[6.3, 8.6]) in the axitinib arm and 4.7 months (95% CI [4.6, 5.6]) in the sorafenib arm, with a hazard ratio of 0.665 (95% CI [0.544, 0.812]) and p-value of <0.0001 (1-sided).

In the subgroup of 251 patients who received prior treatment with cytokines (126 in the axitinib arm and 125 in the sorafenib arm), the median PFS in the axitinib arm was 12.1 months (95% CI [10.1, 13.9]) compared with 6.5 months (95% CI [6.3, 8.3]) in the sorafenib arm, with a hazard ratio of 0.464 (95% CI [0.318, 0.676]) and a p-value of <0.0001 (1-sided). The sorafenib control arm replicated prior Phase 3 sorafenib data (median PFS of 5.5 months) in a cytokine-refractory population. In the subgroup of 389 patients who had received prior treatment with sunitinib-containing regimen (194 in the axitinib arm and 195 in the sorafenib arm), the median PFS in the axitinib arm was 4.8 months (95% CI [4.5, 6.4]) compared with 3.4 months (95% CI [2.8, 4.7]) in the sorafenib arm, with a hazard ratio of 0.741 (95% CI [0.573, 0.958]) and a p-value of 0.0107 (1-sided). The study enrolled only 59 patients who received prior treatment with bevacizumab-containing regimen (29 in the axitinib arm and 30 in the sorafenib arm) and 24 patients who received prior treatment with temsirolimus-containing regimen (12 in the axitinib arm and 12 in the sorafenib arm). Due to small numbers of patients in these subgroups, no firm conclusions can be made.

[figure not shown]

Figure 2 Kaplan-Meier Curve for Progression-Free Survival by Independent Assessment for the Overall Population

Since only a total of 223 patients (approximately 30%) had died as of the data cutoff date (31 August 2010), the data for OS are not mature and likely to change with further followup. As of the data cutoff date, the median OS was not reached in the axitinib arm and was 18.9 months in the sorafenib arm, with a hazard ratio of 1.008 with a 95% CI of (0.774, 1.313) and a 1-sided p-value of 0.525. Further follow-up of OS is continuing.

Table 1 presents adverse reactions reported in patients who received axitinib or sorafenib:

**Table 1** Adverse Reaction (Phase III study)

	Axi	tinib	Sorafenib		
	N=	359	N=355		
Adverse Reaction a	All Grades	Grade 3/4	All Grades	Grade 3/4	
	%	%	%	%	
Diarrhea	55	11	53	7	
Hypertension	40	16	29	11	
Fatigue	39	11	32	5	
Decreased appetite	34	5	29	4	
Nausea	32	3	22	1	
Dysphonia	31	0	14	0	
Palmar-plantar erythrodysesthesia syndrome	27	5	51	16	
Weight decreased	25	2	21	1	
Vomiting	24	3	17	1	
Asthenia	21	5	14	3	
Constipation	20	1	20	1	
Hypothyroidism	19	<1	8	0	
Cough	15	1	17	1	
Mucosal inflammation	15	1	12	1	
Arthralgia	15	2	11	1	
Stomatitis	15	1	12	<1	
Dyspnea	15	3	12	3	
Abdominal pain	14	2	11	1	
Headache	14	1	11	0	
Pain in extremity	13	1	14	1	
Rash	13	<1	32	4	
Proteinuria	11	3	7	2	
Dysgeusia	11	0	8	0	
Dry skin	10	0	11	0	
Dyspepsia	10	0	2	0	
Pruritus	7	0	12	0	
Alopecia	4	0	32	0	
Ervthema	2	0	10	<1	

<sup>aPercentages are treatment-emergent, all-causality events

<sup>b National Cancer Institute Common Terminology Criteria for Adverse Events, Version 3.0

#### 1.2. Rationale

The axitinib response rate in cytokine-refractory patients is higher than reported response rates with cytokines or chemotherapeutics in the second-line setting. Additionally, axitinib response rates in the second-line setting are better than response rates reported in the first-line setting with cytokines or chemotherapeutics alone or in combination. The 5-year survival rate was 20.6% (95% CI, 10.9–32.4%) in patients with mRCC who were refractory to cytokine treatment. Axitinib demonstrated a significantly longer PFS and higher ORR vs sorafenib with an acceptable safety profile as second-line therapy for mRCC. Axitinib was approved by US Food and Drug Administration (FDA) in January 2012 with an indication for the treatment of advanced RCC after failure of one prior systemic therapy. Axitinib was also approved in Japan, Korea and other countries in 2012 for the same indication. The efficacy and safety of axitinib in patients with mRCC support further clinical study to pursue clinical benefits of adjuvant axitinib treatment for patients at high risk of recurrent RCC after nephrectomy.

Risk stratification has become increasingly important in the management of patients newly diagnosed with RCC. Tumor stage is currently the principal prognostic factor for patients with RCC. Although various risk stratification systems have been described, none of them has been accepted as the standard of care. This study aims to recruit those patients who are at a potentially relatively increased risk of disease recurrence. Therefore, the target patients in this study are able to be considered patients at high risk of recurrent RCC.

According NCCN Guidelines v1.2014, adjuvant treatment after nephrectomy currently has no established role in patients with renal cell cancer who have undergone a complete resection of their tumor. No systemic therapy has yet been shown to reduce the likelihood of relapse. Randomized trials comparing adjuvant interferon alpha or high-dose interleukin (IL-2) or cytokines combinations with observation alone in patients who had locally advanced, completely resected RCC showed no delay in time to relapse or improvement in survival with adjuvant therapy. Observation remains standard care after nephrectomy, and eligible patients should be offered enrolled in randomized clinical trials.

Without an established adjuvant treatment for patients with high risk of recurrence of their renal cell cancer after nephrectomy and observation or participation in clinical study as recommended standard; several placebo-controlled, randomized, double blind studies are currently ongoing in this indication (http://clinicaltrials.gov), which is ethically justifiable and necessary to meet regulatory standards for drug approval.

#### 2. TRIAL OBJECTIVES

## 2.1. Primary Objective

• To demonstrate an improvement in disease free survival (DFS) in patients at high risk of recurrent RCC randomly assigned to adjuvant axitinib (Arm A) vs. Placebo (Arm B) after nephrectomy.

## 2.2. Secondary Objectives

- Compare OS associated with Arm A to that associated with Arm B
- Assess safety/toxicity profile of administration of axitinib

[figure not shown]
#### 3. TRIAL DESIGN

This is a prospective, randomized, double-blind placebo controlled Phase 3 trial of oral axitinib starting at 5 mg twice daily vs. placebo given for up to 3 years, with a minimum of 1 year. The dose may be increased or decreased depending on individual patient tolerance of axitinib.

A total of approximately 700 patients will be randomized in a 1:1 ratio between axitinib vs placebo. Patients should begin study treatment within 7 days after randomization. Randomization will occur no sooner than 4 weeks post-nephrectomy and no later than 12 weeks post-nephrectomy.

Follow-up for recurrence (distant or local recurrence of RCC) or occurrence of a secondary malignancy (occurrence of a second primary cancer other than RCC) must be collected at each clinic visit as per protocol. All patients will be followed up (regardless of the duration of treatment) until the time for the final analysis, every 16 weeks for the first 3 years from initiation of study treatment (also, at the end of treatment) and every 6 months thereafter for the remainder of the follow-up period, by clinic visit (See Section 6.4 for further details).

All patients will be followed up for OS status (regardless of the duration of treatment) every 16 weeks until the time for final DFS analysis. Survival status can be ascertained by telephone contact. At the time of final DFS analysis, OS results will be analyzed and summarized.

## 4. SUBJECT SELECTION

The following eligibility criteria are designed to select patients for whom protocol treatment is considered appropriate. All relevant medical and non-medical conditions should be taken into consideration when deciding whether this protocol is suitable for a particular patient.

#### 4.1. Inclusion Criteria

Patients must be newly-diagnosed RCC and treated by nephrectomy (complete or partial) and patients must meet all of the following inclusion criteria to be eligible for enrollment into the trial:

- 1. Patients must have no evidence of macroscopic residual disease or metastatic disease.
- 2. Male or female, age  $\geq 18$  years (age  $\geq 20$  years in Japan, Korea and Taiwan, age  $\geq 18$  years and  $\leq 65$  years in India).
- 3. Patients must be diagnosed with one of the following based on American Joint Committee on Cancer (AJCC) TNM staging version 2010 , Eastern Collaborative Oncology Group (ECOG) performance status (PS). Any Fuhrman grades are eligible. The patient risk groups will be as follows. Group a will be closed for further enrollment, to keep the number of patients of groups b, c, and d with about 90% or more:
  - a. pT2, pN0 or pNx, M0 and ECOG PS 0-1
  - b. pT3, pN0 or pNx, M0 and ECOG PS 0-1
  - c. pT4, pN0 or pNx, M0 and ECOG PS 0-1
  - d. Any pT, pN1, M0 and ECOG PS 0-1
- 4. Patients must have histologically confirmed preponderant, defined as >50%, clear cell RCC.
- 5. Patients must not have received any previous systemic (includes chemotherapeutic, hormonal, or immunotherapeutic) treatment for RCC.
- 6. Patients must not have received any previous anti-angiogenic treatment.
- 7. Patients must have adequate organ function defined as:
  - Absolute neutrophil count (ANC) ≥1500 cells/mm3.
  - Platelets  $\geq$ 75.000 cells/mm3.
  - Hemoglobin (Hgb)  $\geq 9.0$  g/dL.
  - AST and ALT  $\leq 2.5$  x upper limit of normal (ULN).
  - Total bilirubin  $\leq 1.5$  x ULN.
  - Serum creatinine (Scr) ≤1.5 x ULN or calculated creatinine clearance (Clcr) ≥30 mL/min (by the Cockcroft-Gault equation\*).
    - \* For males; the Cockcroft-Gault equation, using Scr : Clcr (mL/min) =  $(140 \text{Age in years}) \times \text{weight (in kilograms)} / [72 \times \text{Scr (in mg/dL)}]$ 
      - The calculated Clcr should be multiplied by 0.85 to adjust for female gender.
  - Urinary protein <2+ by urine dipstick. If dipstick is ≥2+ then a urine protein: urine creatinine ratio (UPC) should be done and the patient may enter only if UPC is < 2.0.

- 8. At screening, no evidence of preexisting uncontrolled hypertension as documented by 2 blood pressure (BP) readings taken at least 1 hour apart in the seated position after the patient has been sitting quietly for 5 minutes. The systolic blood pressure (sBP) readings must be ≤140 mm Hg, and the diastolic blood pressure (dBP) readings must be ≤90 mm Hg. Patients whose hypertension is controlled by antihypertensive therapies are eligible.
- 9. Women of childbearing potential and men must use adequate contraception during the study and for 6 months after discontinuing or completing study treatment. Acceptable contraception for women include implants, injectables, combined oral contraceptives, intrauterine devices (IUDs), sexual abstinence, or a partner who has been vasectomized for at least 6 months. Acceptable contraception for a male includes having had a vasectomy for at least 6 months, sexual abstinence, or condoms plus spermicide.
- 10. Signed and dated informed consent document (ICD) indicating that the patient (or legally acceptable representative) has been informed of all pertinent aspects of the trial prior to enrollment.
- 11. Willingness and ability to comply with scheduled visits, treatment plans, laboratory tests, and other study procedures.

#### 4.2. Exclusion Criteria

Patients presenting with any of the following will not be included in the trial:

- 1. Histologically undifferentiated carcinomas, sarcomas, collecting duct carcinoma, lymphoma, or patients with any metastatic renal sites.
- 2. Active bleeding (other than menstrual bleeding) at randomization.
- 3. Diagnosis of any non-RCC malignancy within the 5 years from date of randomization, except basal cell carcinoma, squamous cell skin cancer, or in situ carcinoma of the cervix uteri that has been adequately treated with no evidence of recurrent disease for 12 months.
- 4. Any of the following within the 12 months prior to study drug administration: myocardial infarction, uncontrolled angina, coronary/peripheral artery bypass graft, symptomatic congestive heart failure, cerebrovascular accident or transient ischemic attack and 6 months for deep vein thrombosis or pulmonary embolism.
- 5. Gastrointestinal abnormalities including:
  - inability to take oral medication
  - requirement for intravenous alimentation
  - prior surgical procedures affecting absorption including total gastric resection
  - treatment for active peptic ulcer disease in the past 6 months

- active gastrointestinal bleeding, unrelated to cancer, as evidenced by hematemesis, hematochezia or melena in the past 3 months without evidence of resolution documented by endoscopy or colonoscopy
- malabsorption syndromes
- chronic diarrhea that persists at Grade 3 or 4 despite maximal medical therapy
- 6. Major surgery <4 weeks, or radiation theapy <2 weeks, of starting the study treatment or incomplete healing of surgical or superficial wounds.
- 7. Current use or anticipated need for treatment with drugs that are known potent CYP3A4/5 inhibitors (eg, grapefruit juice, ketoconazole, itraconazole, clarithromycin, atazanavir, indinavir, nefazodone, nelfinavir, ritonavir, saquinavir, and telithromycin).
- 8. Current use or anticipated need for treatment with drugs that are known CYP3A4/5 or CYP1A2 inducers (eg, rifampin, dexamethasone, phenytoin, carbamazepine, rifabutin, rifapentin, phenobarbital, and St. John's wort).
- 9. Active seizure disorder or evidence of brain metastases, spinal cord compression, or carcinomatous meningitis.
- 10. A serious uncontrolled medical disorder or active infection that would impair their ability to receive study treatment.
- 11. Known human immunodeficiency virus (HIV) or acquired immunodeficiency syndrome (AIDS)-related illness.
- 12. Pregnancy or breastfeeding. Urinary pregnancy test should be performed by sites on female patients who have not experienced at least one consecutive year of amenorrhea without ovarian dysfunction, or have been taking hormonal therapy, or have been rendered surgically sterile. If positive, serum pregnancy test should be performed at central laboratories. All female patients of childbearing potential must have a negative pregnancy test within the 14 days prior to date of randomization. (Definition of surgical sterilization: patients who underwent hysterectomy or bilateral oophorectomy, or bilateral tubal ligation)
- 13. Dementia or significantly altered mental status that would prohibit the understanding or rendering of informed consent and compliance with the requirements of this protocol.
- 14. Other severe acute or chronic medical or psychiatric condition or laboratory abnormality that may increase the risk associated with study participation or study drug administration, or may interfere with the interpretation of study results, and in the judgment of the investigator would make the patient inappropriate for entry into this study.
- 15. Receipt of any investigational oncology or, approved or investigational anti-angiogenic agent prior to study entry.

16. Current treatment on another therapeutic clinical trial. Supportive care trials or non-treatment trials, eg, Patient Reported Outcomes (PRO) methods studies, are allowed

#### 4.3. Randomization Criteria

Patients must be randomized no earlier than 4 weeks and no later than 12 weeks after nephrectomy and treatment should be started within 7 days after randomization. Patient eligibility must be confirmed by independent review committee (IRC) assessment of imaging by a sponsor designated center prior to randomization.

Patients must be randomized based on the assessment by the IRC when there is a discrepancy between the local and the IRC imaging review.

A centralized system will be used to assign patient numbers and randomize patients into blinded study drug: axitinib, or blinded placebo identical in appearance to the active study drug.

After a patient has provided written informed consent and has completed the necessary screening assessments, the clinical site must contact a centralized internet/telephone registration system (IWRS/IVRS), to enroll the patient into study.

For those patients who failed screening, the reason for screen failure should be entered in the source documentation. The following information should also be collected in the source documents: Patient age, sex, ECOG PS, tumor size (eg, T1, T2, T3), nodal disease (Yes/No), metastatic disease (Yes/No), histological type (eg, clear cell).

At the time of registration, the clinical site staff must provide site and patient identifiers and demographic information. The registration system will assign a unique patient identification number. The system will also be used to assign blinded study drug bottles. Patients will be randomized to one of two arms:

Arm A: axitinib 5 mg BID taken orally (doses should be taken approximately 12 hours apart continuous dosing)

Arm B: Placebo tablets BID taken orally

Patients will be stratified by:

- 1. Risk group
  - a. pT2, pN0 or pNx, M0 and ECOG PS 0-1
  - b. pT3, pN0 or pNx, M0 and ECOG PS 0-1
  - c. pT4, pN0 or pNx, M0 and ECOG PS 0-1
  - d. Any pT, pN1, M0 and ECOG PS 0-1
- 2. Country

Eligible patients will be randomized in a 1:1 ratio to one of the two treatments using the registration system. Patients in risk group a or b will be stratified by risk group and by country. Patients in risk group c or d will be stratified by risk group only.

Randomization shall continue until a minimum of 10% of subjects are represented in this study from groups c and d. Risk group a will be closed for from further enrollment, to keep the number of patients of risk groups b, c, and d with about 90% or more.

## 4.4. Life Style Guidelines

During the study female patients of childbearing potential must take precautions to prevent pregnancy since the effects on the fetus are unknown. Male patients with partners of childbearing potential must take precautions to prevent pregnancy of the partner since the effects of these drugs on sperm are unknown. These restrictions should remain in force for 6 months from the last dose of investigational agent. Drug interaction studies with oral contraceptives have not been performed, so barrier methods of contraception or abstinence should be considered. Adequate contraception should be discussed with the investigator before the treatment start and should be in agreement with local law.

#### **5. TRIAL TREATMENTS**

#### 5.1. Allocation to Treatment

Axitinib for up to 3 years, with a minimum of 1 year until recurrence, occurrence of a secondary malignancy, significant toxicity, or withdrawal of consent.

#### OR

Placebo for up to 3 years, with a minimum of 1 year until recurrence, occurrence of a secondary malignancy, significant toxicity, or withdrawal of consent.

## 5.2. Breaking the Blind

At the initiation of the trial, the trial site will be instructed on the method for breaking the blind. The method will be an electronic process. Blinding codes should only be broken in emergency situations for reasons of patient safety, or if the patient has a confirmed recurrence or occurrence of a secondary malignancy with limited alternative treatment option and knowledge of study drug is required to facilitate further treatment decision. For those with suspected recurrence, the site must await results from the Independent Review Committee (IRC). The decision to break the blind must be approved by the Sponsor prior to doing so. When the blinding code is broken, the reason must be fully documented in the site source document.

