**3.2.3. Blinding**

The study is double-blind. Axitinib will be supplied as 1 mg and 5 mg film-coated tablets for oral administration in light-protecting bottles. Placebo will match all dose formulations and will be identical in appearance to the active study drug.

At the initiation of the trial, the trial site will be instructed on the method for breaking the blind. The method will be an electronic process. Blinding codes should only be broken in emergency situations for reasons of subject safety, or if the subject has a confirmed recurrence or occurrence of a secondary malignancy with limited alternative treatment option and knowledge of study drug is required to facilitate further treatment decisions. For those with suspected recurrence, the site must await results from the IRC. The decision to break the blind must be approved by the Sponsor prior to doing so. When the blinding code is broken, the reason must be fully documented in the site source document. In these instances, only the principal investigator (PI) is unblinded. The broader study team will remain blinded.

Where unblinded study data is to be produced for review by the DMC for the study, a biostatistics team in a separate location from the study team will be used to produce and distribute the unblinded data. The data will only be distributed to unblinded personnel as agreed in a separate DMC analysis plan and/or DMC charter.

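### Protocol 5.2 and SAP 3.2.3 require prior Sponsor approval for every code break and do not exempt patient-safety emergencies

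*Protocol*

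**What the plan says.** Protocol 5.2 says that sites are taught at trial start how to break the blind, and that "The method will be an electronic process". It then gives two grounds.

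- Emergency: "Blinding codes should only be broken in emergency situations for reasons of patient safety".
- Recurrence or secondary malignancy: the event is confirmed, few other treatment options remain, and "knowledge of study drug is required to facilitate further treatment decision".

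Two conditions follow. The first is about waiting for the imaging review: "For those with suspected recurrence, the site must await results from the Independent Review Committee (IRC"). The second is about approval: "The decision to break the blind must be approved by the Sponsor prior to doing so". The section ends by requiring the reason for the break to be recorded in the site's source documents.

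SAP 3.2.3 gives the same two grounds and the same approval sentence. It adds: "In these instances, only the principal investigator (PI) is unblinded", with the wider study team staying blinded.

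**The concern.** The two grounds differ in urgency. Once recurrence or a second cancer is confirmed, the choice of next treatment usually leaves time for a request and a reply, so a Sponsor check on whether the assignment is really needed is reasonable. An emergency code break exists for situations in which waiting is the problem.

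One approval rule over both grounds makes the emergency ground depend on an answer from someone who is not treating the patient. A site that follows the text waits. A site that acts first departs from the protocol, even though the same paragraph recognises its reason for acting. Patient safety and consistent conduct across sites are at stake; the DFS analysis is not.

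**Working it through.** No arithmetic applies, because the point depends on no event count, effect size, alpha or power. The check is whether the approval sentence reaches the emergency ground and whether anything elsewhere releases it.

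**1. Scope of each sentence in Protocol 5.2**

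| Sentence | Scope that it states |
|---|---|
| Emergency ground | Emergencies, for patient safety |
| Recurrence or secondary-malignancy ground | Confirmed event, few alternatives, assignment needed |
| Wait for the Independent Review Committee (IRC) | Suspected recurrence only |
| Prior Sponsor approval | None stated: any decision to break the blind |
| Record the reason | Whenever the code is broken |

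The IRC sentence names the patients to whom it applies. The approval sentence, which comes next, names none. On a plain reading it therefore covers both grounds.

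**2. Does the SAP narrow it?** No. SAP 3.2.3 repeats the approval sentence without restriction. Its added sentence says who learns the assignment; it does not change who must agree beforehand.

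**3. Is there an exemption elsewhere?** Three parts of the protocol could hold one: dose interruption and reduction (5.3.4), patient withdrawal (6.5) and adverse event reporting (section 8). None contains an emergency exception to the approval rule, a maximum time for the Sponsor to reply, or a statement that the investigator may unblind first and report afterwards.

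**4. How does the protocol treat urgency in other places?**

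- Sections 5.5.2, 6.5.1 and 7.1 encourage investigators to wait for the IRC before deciding on treatment, but release them when the clinical situation needs action at once, with brain metastases as the example.
- Section 12.1 lets an amendment start before ethics approval when it removes an apparent immediate hazard, with written notice within 5 working days afterwards.
- Section 8.12.1 has serious adverse events reported to the Sponsor within 24 hours of the investigator becoming aware of them, that is, after the fact.

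In the first two, the protocol sets a wait or an approval and writes the urgent exception beside it. Section 5.2 sets an approval and writes none.

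**The case against.** The best reply is that the approval sentence was meant only for the recurrence route. It comes straight after the sentence on suspected recurrence, and that route is the discretionary one, where Sponsor review makes sense. This is a fair reading of intent. It does not settle the matter, because the sentence carries no such limit in the protocol and the SAP repeats it in the same open form. If that was the intent, the change below only puts it into words.

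A second reply is that site instructions, or the contact pages missing from the public copy, may give an emergency route. They may, and their absence from this copy is no fault in the plan. But a telephone number would not alter the approval rule, and an instruction that dispensed with approval would contradict section 5.2.

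A third reply is that the foreseeable serious events can be managed blind. This largely stands. Section 5.3.4 sets rules in axitinib/placebo terms for reversible posterior leukoencephalopathy, for grade 3 arterial, hemorrhagic and perforation events, and for hypertension, and none of those rules depends on the arm. A reader might infer that these events could not be treated safely without the code; the documents do not support that. What remains is that section 5.2 itself foresees emergencies in which the code may be broken, and the approval step falls on exactly those.

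**Conclusion.** The point holds as a gap in the written rule. Both documents permit emergency unblinding and then require prior Sponsor approval for any unblinding, without an exception. This rests on reading the approval sentence as it stands and on the absence of an exemption in the two documents. It applies to every patient (approximately 700) for up to 3 years of treatment. How often it would matter is unknown, since no emergency unblinding rate is given. No effect on the DFS comparison is claimed.

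Four stronger conclusions might be inferred, and the documents do not support them.

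- That a site is physically unable to unblind: neither document says that the electronic system withholds the code until the Sponsor agrees. The obstacle shown is a rule.
- That approval would often be delayed out of hours: SAP 3.2.2 lists nine countries or regions for stratification, but nothing gives the location or hours of Sponsor staff.
- That Sponsor involvement threatens the study team's blind: agreeing to a code break does not reveal the arm, and SAP 3.2.3 keeps the wider team blinded.
- That the 16% rate of grade 3/4 hypertension with axitinib in protocol Table 1 measures the need: it comes from a second-line trial in metastatic disease and is not a rate of emergencies or of unblinding.

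**What to change.** Make the same change in Protocol 5.2 and SAP 3.2.3:

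- Limit prior Sponsor approval to the confirmed recurrence or secondary-malignancy route.
- State that in a patient-safety emergency the investigator may break the code directly through the electronic process.
- Require prompt notice to the Sponsor afterwards, without stating the arm.
- Keep the existing requirement to document the reason in the source record.

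The cost is about one sentence in each document, with site instructions brought into line if they say otherwise. The downside is that a few more code breaks may happen without prior review. The documented reason and the notice afterwards let the Sponsor examine each one.
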